### **10.3 Recording Adverse Events**

Adverse events (including pre-treatment adverse events) and adverse drug reactions must be recorded on an *Adverse Event Form*. The investigator must provide information on the adverse event / drug reaction, preferably with a diagnosis, or at least with signs and symptoms; start and stop dates; intensity; causal relationship to the IMP; action taken; and outcome. If the adverse event is not related to the IMP, an alternative etiology must be recorded, if available. If the adverse event is an overdose, the nature of the overdose must be stated (for example, medication error, accidental overdose, or intentional overdose). If the intensity changes during the course of the adverse event, this must be recorded on the *Adverse Event Form*.

If the adverse event is *serious*, this must be indicated on the *Adverse Event Form*. Furthermore, the investigator must report the SAE to Lundbeck immediately (within 24 hours) after becoming aware of it (see section [10.4](#)).

If individual adverse events are later linked to a specific diagnosis, the diagnosis should be reported and linked to the previously reported adverse events.

### **10.4 Reporting Serious Adverse Events**

The investigator must report SAEs to Lundbeck immediately (within 24 hours) after becoming aware of them by completing the *Adverse Event Form* in the eCRF.

The initial entry of the SAE in the *Adverse Event Form* must contain as much information as possible and, if more information about the patient's condition becomes available, the *Adverse Event Form* must be updated with the additional information.

If the investigator cannot report the SAE in the eCRF within 24 hours of becoming aware of the event, then he or she must complete and sign the *Serious Adverse Event Fallback Form* and send it to Lundbeck Global Patient Safety, US at:

[contact]  
email: [gpusu\\[contact]](mailto:[contact])

Lundbeck will assume responsibility for reporting SAEs to the authorities in accordance with local requirements.

It is the investigator's responsibility to be familiar with local requirements regarding reporting SAEs to the IRB and to act accordingly.

## **10.5 Treatment and Follow-up of Adverse Events**

Patients with adverse events must be treated in accordance with usual clinical practice at the discretion of the investigator.

The investigator must follow up on non-serious adverse events until resolution or the Safety Follow-up Visit, whichever comes first. At the Safety Follow-up Visit, information on new SAEs, if any, and stop dates for previously reported adverse events must be recorded.

The investigator must follow up on all SAEs until the patient has recovered, stabilized, or recovered with sequelae, and report to Lundbeck all relevant new information using the same procedures and timelines as those for the initial *Serious Adverse Event Form*.

SAEs that are spontaneously reported by a patient to the investigator within 30 days after the Safety Follow-up Visit must be reported to Lundbeck via the e-mail address noted in Section 10.4. In this case, an e-mail describing the reported SAE will be sufficient; Lundbeck Global Patient Safety US will follow-up should additional information be required.

These SAEs will be recorded in the Lundbeck safety database.

# **11 Data Handling and Record Keeping**

## **11.1 Data Collection**

### **11.1.1 Electronic Case Report Forms**

eCRFs will be used to collect the data related to the study as collected by the Investigators (or designees) at study visits (see [Panel 4](#)).

The eCRFs use third party software to capture data via an online system on a device. When the investigator enters data in the eCRF (ideally during the visit or as soon as possible [ $<3$  days] thereafter), the data will be securely transmitted to a central database over a secured web server, and all entries and modifications to the data will be logged in an audit trail.

Access to the system will only be granted after appropriate and documented training. Written instructions for using the system will be provided along with the training.

Electronic signatures will be used where signatures are required on pages and/or visits. Automated data entry checks will be implemented where appropriate; other data listings may be reviewed and evaluated for accuracy by the sponsor and/or representatives from the CRO. All entries, corrections, and changes must be made by the investigator or a delegate.

### **11.1.2 Electronic Diary (eDiary)**

An eDiary, which is an app that will be downloaded to each participant's smart phone or tablet, will be used to collect information from the participants throughout the course of the study, from Visit 1 through Visit 8 (see [Panel 1](#), [Panel 2](#) and [Panel 3](#)).

The eDiary uses third party software to capture data via an online system on a mobile device. When the participant enters data in the eDiary, the data will be transmitted via a protected SSL to a central database where it will be securely stored, and all data entries will be logged in an audit trail. No entries will be able to be modified, once entered. Participants will be provided instructions on how to use the eDiary at Visit 1 by the site staff. Access to the system (for site staff, CRO staff and Lundbeck staff) will only be granted after appropriate and documented training.

### **11.1.3 Patient Data**

#### **11.1.3.1 Recording of Patient Data**

All participant data collected by a participating site will be documented in the participant's medical record or a study-specific record (paper or electronic format) and will contain information to support all data entered into the EDC.

#### **11.1.3.2 Clinical Outcome Assessments**

Clinical outcomes will be recorded by participating sites into the EDC system as per [Panel 4](#)

#### **11.1.3.3 Serious Adverse Event Fallback Forms**

*Serious Adverse Event Fallback Forms* must be used when the eCRF cannot be accessed.

### **11.1.4 External Data**

All electronic data will be transferred using a secure method accepted by Lundbeck.

The following electronic data will be transferred by the CRO / third-party vendor and kept in a secure designated storage area outside the eCRF:

- eDiary data

## 11.2 Retention of Study Documents at the Site

### 11.2.1 eCRF data

If a site closes before the study has been completed, the investigator will continue to have read-only access to the eCRF until the study has been completed. The change to read-only status will take place once all data for the site has been reviewed and the forms have been locked. After the study has been completed, all user access to the eCRF will be revoked. Renewed access to the eCRF will be given if corrections or updates to the database are required.

At the end of the study, the site will be provided with all data related to the site (including eCRF data, queries, and the audit trail) using a secure electronic medium; the secure storage of these data at the site is the responsibility of the investigator. When confirmation of receipt of the data has been received from all sites, all user access to the eCRF will be revoked. If, for some reason, the data are not readable for the full retention period (25 years or in accordance with national requirements, whichever is longer), the investigator may request that the data be re-sent by the sponsor.

### 11.2.2 Other Study Documents

The investigator must keep the investigator's set of documents in the investigator TMF / Essential Documents Binder for at least 25 years after the *Clinical Study Report* has been approved or in accordance with national requirements, whichever is longer. Lundbeck will remind the investigator in writing of this obligation when the *Clinical Study Report Synopsis* is distributed to the site.

If off-site storage is used, a study-specific binder will remain at the site after the other study-specific documents have been shipped for off-site storage. This binder is considered part of the investigator TMF and must be kept in a secure place by the site for the required period of time. The binder must contain, at a minimum, the following documents: a copy of the *Investigator TMF Index*, a certified copy of the *Patient Identification Code List*, and a *Retrieval Form*.

When the required storage period has expired, the documents may be destroyed in accordance with regulations.

## 12 Monitoring Procedures

During the study, the CRO will review the study data on an ongoing basis to identify incorrect, inconsistent, and missing data. Any discrepancies or clarifications will be identified and directed to the sites using the query tool within the EDC system. Sites will be required to respond to all generated queries sufficiently before the query can be closed.

## 13 Audits and Inspections

Authorized personnel from Medical, Regulatory and Clinical Quality Assurance, H. Lundbeck A/S, and quality assurance personnel from business partners may audit the study at any time to assess compliance with the protocol and the principles of *Good Clinical Practice* and all other relevant regulations.

The investigator must be aware that representatives from regulatory authorities may also wish to inspect source data, such as medical records. The investigator must notify Lundbeck, without delay, of an announced inspection by a regulatory authority.

During audits and inspections, the investigator must permit direct access to all the source documents, including medical records and other documents pertinent to the study.

During audits and inspections, the auditors and inspectors may request relevant parts of medical records. No personal identification apart from the screening numbers will appear on these copies.

Patient data will not be disclosed to unauthorized third parties, and patient confidentiality will be respected at all times.

## 14 Protocol Compliance

Lundbeck has a “no-waiver” policy, which means that permission will not be given to deviate from the protocol.

If a deviation occurs, the investigator or designee must inform the CRO and they must review, discuss, and document the implications of the deviation.

## 15 Study Termination

Lundbeck or a pertinent regulatory authority may terminate the study or part of the study at any time. The reasons for such action may include, but are not limited to, safety concerns.

If the study is terminated or suspended, the investigator must promptly inform the patients and ensure appropriate therapy and follow-up. Furthermore, the investigator and/or sponsor must promptly inform the IRB and provide a detailed written explanation. The pertinent regulatory authorities must be informed in accordance with national regulations.

If the risk/benefit evaluation changes after the study is terminated, the new evaluation must be provided to the IRB if it will have an impact on the planned follow-up of the patients who participated in the study. If so, the actions needed to protect the patients must be described.

## 16 Statistical Methodology

### 16.1 Responsibilities

Biostatistics, Lundbeck LLC, will perform the statistical analyses for this study.

### 16.2 Analysis Population

The eligible population will comprise all participants who give their informed consent and met the selection criteria. All participants completing at least one daily report after receiving their initial treatment at the Baseline Visit will be considered in the analysis sample. All data collected from participants who withdraw from the study will be collected up until the date of the withdrawal.

The safety population will consist of all participants who receive at least one infusion of eptinezumab.

### 16.3 Safety Analyses

#### 16.3.1 Analysis of Adverse Events

Adverse event and adverse drug reaction data will be tabulated and reported. No additional analyses are planned.

#### 16.3.2 Sample Size and Power

EVEC is an exploratory study, as such the sample size was considered secondary to the ability of the study to provide exploratory information concerning the objectives. However, for illustrative purposes we provide the power analysis here. Based upon the PROMISE trials and Phase IIIa studies of other medications to be evaluated in EVEC we expect to see a 2-day difference in the average monthly migraine days (MMD) at 13 weeks and a standard deviation of 6.0 around this measure. Based on this we expect to have 83% power to assess this difference with a sample size of 200 participants, assuming no significant loss to follow-up.

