As would be expected in a pragmatic trial, the sample size of EVEC (100 persons per arm) is a function of the project budget and timeliness. In [Panel 6](#) we illustrate the expected power based upon the assumptions developed from PROMISE 1 and 2. We have highlighted the 100 per arm for the PROMISE 2 effect size. If, as expected, we meet the PROMISE 2 assumptions, we will have at least 72% power to demonstrate a standardized effect of 0.45. Given that we believe that the effect size will be larger in EVEC than observed in PROMISE 2, even as we pool patients with episodic and chronic migraine, we expect to have a practical power in excess of 80% to find a difference between eptinezumab and the other advanced preventive medications with an alpha of 0.05.

16 Statistical Software

Analyses will be conducted using SAS[®], Version 9.4 or later and R[®], Version 4.2.1 or later.

17 Changes to Analyses Specified in the Protocol

N/A

18 Details on Data Handling

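### The 83% power in Protocol 16.3.2 does not follow from its printed inputs (65% unadjusted), and SAP 15.1 pairs 72% with the wrong effect size and gives no calculation for its claim of more than 80%

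*Protocol*

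**What the plan says.** Protocol 16.3.2 expects a 2-day difference in average monthly migraine days at 13 weeks with an SD of 6.0. From this it concludes: "we expect to have 83% power to assess this difference with a sample size of 200 participants". The calculation makes no allowance for dropout. It gives no alpha, sidedness, test, covariate adjustment or correlation, and it is introduced with "for illustrative purposes we provide the power analysis here".

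SAP 15.1 covers the same ground differently. Panel 5 lists standardized effects of eptinezumab against placebo: at 100 mg, 0.23 in PROMISE 1 and 0.36 in PROMISE 2; at 300 mg in PROMISE 2, 0.45. Panel 6 gives power at 100 per arm of 37%, 56% and 72% for effects of 0.23, 0.30 and 0.36. The text points to the PROMISE 2 row at 100 per arm and states: "we will have at least 72% power to demonstrate a standardized effect of 0.45". It goes on to express a belief in a larger effect than PROMISE 2 showed, and from that it concludes: "we expect to have a practical power in excess of 80% to find a difference between eptinezumab and the other advanced preventive medications". The significance level is given as 5%. The SAP also says that the size of 100 per arm "is a function of the project budget and timeliness".

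**The concern.** For the same 100 per arm, a reader meets three power statements that do not agree: 83%, at least 72% at an effect of 0.45, and more than 80%. The protocol's effect of 2/6.0 = 0.33 lies between two Panel 6 rows (0.30 and 0.36) whose power at 100 per arm is 56% and 72%, so 83% is outside the range that the SAP's own table allows.

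At stake is the reading of the results. SAP 11.2.2 tests most of its comparative endpoints at p<0.05. Anyone judging a null finding will look to these sections for what difference the study could have detected, and will not find a consistent answer.

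**Working it through.** **Inputs.** Difference 2 days, SD 6.0, N = 200 (Protocol 16.3.2). 100 per arm and alpha 0.05 (SAP 15.1). Two-sided tests (SAP 11.2.2). Equal arms fit the design: episodic migraine is randomized 1:1, and chronic migraine 3:2:1, which pools to 3:3 for eptinezumab against all comparators.

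**Step 1: the SAP's own table.** Unadjusted normal approximation: power = Φ(d·√(n/2) − 1.96), with d the standardized effect and n the number per arm.

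| Effect d | n = 100 | n = 150 | n = 200 | Panel 6 prints |
|---|---|---|---|---|
| 0.23 | 36.9% | 51.3% | 63.3% | 37 / 51 / 63 |
| 0.30 | 56.4% | 73.8% | 85.1% | 56 / 74 / 85 |
| 0.36 | 72.1% | 87.7% | 95.0% | 72 / 88 / 95 |

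All nine cells match, so Panel 6 uses two-sided 5% without adjustment.

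**Step 2: the protocol's inputs.** d = 2/6.0 = 0.333; d·√(100/2) = 2.357; Φ(2.357 − 1.96) = 65.4%. The noncentral t gives 65.0%. One-sided 5% gives 76%. Neither is 83%.

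**Step 3: what 83% would need.** Any one of these, holding the other inputs fixed (t-test):
- about 154 per arm (153 gives 82.8%, 154 gives 83.0%);
- a difference of about 2.48 days;
- an effective SD of about 4.83.

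**Step 4: routes that could lower the SD.** The correlations below are assumptions; the documents give none.
- *Baseline adjustment*, SD = 6.0·√(1 − r²): r = 0.5 gives 77%, r = 0.59 gives 83%, r = 0.6 gives 83%.
- *Three-month mean*, if 6.0 is a single-month SD, SD = 6.0·√((1 + 2ρ)/3): ρ = 0.47 gives SD 4.82 and 83%; 0.5 gives 82%, 0.6 gives 78%, 0.8 gives 71%. If 6.0 already describes the average, this route adds nothing.
- *Both together*, again with a single-month SD of 6.0, SD = 6.0·√((1 + 2ρ)/3 − b²), where b is the correlation of baseline with each follow-up month: ρ = 0.6, b = 0.3 gives 83%; 0.7, 0.4 gives 83%; 0.8, 0.5 gives 85%; 0.8, 0.3 gives 76%. If baseline and all follow-up months share one correlation, the SD does not exceed 4.0 and power is at least 94%.

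**Step 5: the SAP text.** At d = 0.45 and 100 per arm, 0.45·√50 = 3.182 and Φ(3.182 − 1.96) = 88.9% (t: 88.6%). So 72% goes with 0.36, and 0.45 goes with 89%. At 100 per arm, 80% power needs d of about 0.40, which is 0.398 × 6.0 = 2.39 days at the protocol's SD.

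**Step 6: consistency with the analysis sections.** SAP 15.1 presents a regression of cumulative migraine days as the test of a primary hypothesis. No outcome analysis in SAP 11.2 fits that model: post-baseline migraine days appear only in the 11.2.7 correlations, and pre-study migraine days are a covariate in 11.2.8. Protocol 3.3 says there is no primary objective.

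**The case against.** The strongest reply is that 83% may be right for a model the protocol did not write down. Section 16.3.2 states no test or adjustment, and the regression in SAP 15.1 has both a cumulative outcome and a baseline covariate. Step 4 shows that this combination can reach or pass 83% at moderate correlations if 6.0 is a single-month SD. This stands as a possibility, and it is why 65% must carry the word unadjusted. It does not rescue the text: the protocol derives 83% from the difference and SD alone, and neither document gives a correlation or reduced variance. Panel 6, the only power table, uses no adjustment.

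On the 72% figure, the SAP says at least 72%, which is literally true at 0.45 and understates power there. It is best read as a mislabelled effect size, but it still contradicts the row it cites.

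On the claim of more than 80%, the SAP says openly that it rests on an expected larger effect, and the 300 mg value of 0.45 would give 89%. But the SAP expects most patients to start on 100 mg, where Panel 5 has 0.23 and 0.36. Those effects are against placebo, while this study has only active comparators. No figure explains why the difference should be larger here.

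Finally, the analysis is labelled illustrative, all objectives are exploratory, and monthly migraine days were removed as an outcome and kept as a mediating factor. That may explain the leftover regression model, and it limits the consequence. It does not make the figures consistent.

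**Conclusion.** The concern holds. The protocol's 83% is 18 points above the 65% that its printed inputs give at 100 per arm, two-sided 5%, unadjusted; even one-sided testing gives only 76%. Alpha and sidedness come from the SAP because the protocol states neither. An unstated adjustment or cumulative outcome could justify 83%, but nothing in the documents lets a reader check it. In the SAP, 72% belongs to an effect of 0.36; the 0.45 it is paired with gives 89%, 17 points higher. The expectation of more than 80% has no supporting calculation and needs an effect of about 0.40, above both 100 mg values in Panel 5. This should be fixed, but its reach is limited: sample size, endpoints and tests do not depend on these figures.

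**What to change.** **Protocol 16.3.2.** Either replace 83% with 65% (two-sided 5%, unadjusted, 100 per arm), or keep 83% and state the test, the adjustment and the correlation or variance assumption that produces it. If an adjusted model was in fact used, the second option is the right one.

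**SAP 15.1.** State 72% for a standardized effect of 0.36 and 89% for 0.45. Replace the claim of more than 80% with the effect that 80% power requires at 100 per arm, about 0.40. Add that the placebo-controlled effects in Panel 5 may overstate the difference against active comparators. Label the migraine-day regression as illustrative planning only.

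**Cost.** One protocol sentence and one SAP section, with no change to sample size, design or analyses. The stated power becomes less favourable unless the missing assumptions are supplied. The protocol change needs an amendment, which may require informing the IRB under Protocol 4.4.

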### 16.4 Statistical Analysis Plan

A *Statistical Analysis Plan* describing the handling of data issues and the planned statistical analyses in more detail will be prepared by Lundbeck LLC, before the study is completed.

## 17 Clinical Study Report and Publications

### 17.1 Data Ownership

The data collected in this study are the property of Lundbeck.

### 17.2 Clinical Study Report

Upon completion of the study, a *Clinical Study Report* will be prepared by Regulatory Medical Writing, Lundbeck LLC.

### 17.3 Summary of Clinical Study Results

Upon completion of the study and when the study results are available, the patient has the right to be informed by the investigator about the overall study results.

### 17.4 Publications

The results of this study will be submitted for publication.

Lundbeck will submit results information to ClinicalTrials.gov for this study.

The primary publication based on this study must be published before any secondary publications. Authors of the primary publication must fulfil the criteria defined by the ICMJE.

## 18 Indemnity and Insurance

In the event of study-related injuries or deaths, insurance for the patients and indemnity of the investigators and those of their employees, servants, or agents whose participation in this study has been documented are provided. Insurance and liability will be in accordance with applicable laws and *Good Clinical Practice*.

## 19 Finance

### 19.1 Site Agreements

The financial agreements with each site are addressed in one or more documents. Both parties must sign the agreements before each site is initiated.

### 19.2 Financial Disclosure

All the investigators, including sub-investigators, participating in the study must complete a *Financial Disclosure Form*

## Appendix II

# The American Headache Society Position Statement on Integrating New Migraine Treatments into Clinical Practice

Headache  
© 2018 American Headache Society

ISSN 0017-8748  
doi: 10.1111/head.13456  
Published by Wiley Periodicals, Inc.

## AHS Consensus Statement

### The American Headache Society Position Statement On Integrating New Migraine Treatments Into Clinical Practice

American Headache Society

**Objective.**—To provide healthcare professionals with updated guidance in the use of novel preventive and acute treatments for migraine in adults.

**Background.**—The principles of preventive and acute pharmacotherapy for patients with migraine have been outlined previously, but the emergence of new technologies and treatments, as well as new formulations of previously established treatments, has created a need for an updated guidance on the preventive and acute treatment of migraine.

**Methods.**—This statement is based on a review of existing guidelines and principles for preventive and acute treatment of migraine, as well as the results of recent clinical trials of drugs and devices for these indications. Input was sought from health insurance providers, employers, pharmacy benefit service companies, device manufacturers, pharmaceutical and biotechnology companies, patients, and patient advocates. Expert clinicians and researchers in the field of headache medicine from across North America and the European Union provided input and feedback.

**Results.**—The principles of pharmacologic preventive treatment of migraine with oral treatments have been as follows: use evidence-based treatments when possible and appropriate; start with a low dose and titrate slowly; reach a therapeutic dose if possible; allow for an adequate treatment trial duration; establish expectations of therapeutic response and adverse events; and maximize adherence. Newer injectable treatments may work faster and may not need titration. The principles of acute treatment include: use evidence-based treatments when possible and appropriate; treat early after the onset of a migraine attack; choose a nonoral route of administration for selected patients; account for tolerability and safety issues; consider self-administered rescue treatments; and avoid overuse of acute medications. Neuromodulation and biobehavioral therapy may be appropriate for preventive and acute treatment, depending on the needs of individual patients. Neuromodulation may be useful for patients who prefer nondrug therapies or who respond poorly, cannot tolerate, or have contraindications to pharmacotherapy.

**Conclusions.**—This statement updates prior recommendations and outlines the indications for initiating, continuing, combining, and switching preventive and acute treatments of migraine.

**Key words:** migraine, treatment, acute, preventive, principles

**Abbreviations:** AE adverse event, CBT cognitive behavioral therapy, CGRP calcitonin gene-related peptide, DHE dihydroergotamine, FIS Functional Impairment Scale, HIT Headache Impact Test, HRQoL health-related quality of life, ICHD International Classification of Headache Disorders, IM intramuscular, IV intravenous, mAbs monoclonal antibodies, MFIQ Migraine Functional Impact Questionnaire, MHD monthly headache day, MIDAS Migraine Disability Assessment, Migraine-ACT Migraine Assessment of Current Therapy, MMD monthly migraine day, MPFID Migraine Physical Function Impact Diary, MSQ Migraine-Specific Quality of Life, mTOQ Migraine Treatment Optimization Questionnaire, NSAID nonsteroidal anti-inflammatory drug, PGIC Patient Global Impression of Change, PPMQ-R Patient Perception of Migraine Questionnaire-Revised, SC subcutaneous, WPAI Work Productivity and Activity Impairment

*(Headache 2019;59:1-18)*

From the American Headache Society.

Address all correspondence to [name], American Headache Society, [name], USA, email: [[contact]](mailto:[contact])

Accepted for publication October 26, 2018.

*Conflict of Interest:* No funding was received to support the development of drafting of this manuscript.

